1. SUMMARY

Study title: ConnectBack Trial – Creating Team-Based care for a new primary care model for low back pain: A cluster randomised trial

Protocol version: 2024/1.8

Objectives:

Overarching objective

To evaluate whether integrating a musculoskeletal (MSK) clinician (physiotherapist/chiropractor) within primary care teams for people with low back pain (LBP) and making this clinician available to LBP patients as an early point of contact, will improve outcomes.

Specific objectives

The specific aims are to determine whether a new model of care for people presenting to primary care with LBP, incorporating a team-based approach, is more effective than usual general practitioner (GP)-led care, evaluated over a one-year period, for:

- 1) disability (primary outcome at 3 months), pain intensity, quality of life, global rating of change, patient satisfaction, and adverse events.
- 2) health system and societal outcomes, including healthcare access, GP workload, emergency department visits, diagnostic imaging, opioid medications used, and missed work.
- 3) cost-effectiveness.

Further, a process evaluation will assess the implementation of the model of care and the perspectives of patients and primary care providers towards the model.

Study design:

The trial is a parallel arm cluster randomised trial (CRT) with 20 primary care practices randomised 1:1 to either an innovative primary care model of care incorporating a team-based approach, or to usual GP-led care for low back pain (LBP).

Planned sample size:

Twenty GP practice sites will recruit a total of 1,560 participants.

Selection criteria:

Practice inclusion criteria: At least 2 GPs from the practice are willing to participate; and the practice can accommodate a trial MSK clinician to coordinate patient treatment.

Practice exclusion criteria: The practice already has an integrated MSK clinician (physiotherapist or chiropractor) onsite.

GP inclusion criteria: GP works in an eligible practice, and the GP is willing for their practice to be randomised to the intervention or usual care arm.

GP exclusion criteria: working in a practice that already has a physiotherapist/chiropractor integrated into the team.

Patient inclusion criteria: adults (≥ 18 years) with LBP of any duration (with or without associated leg pain), who can read, write, and speak in English.

Patient exclusion criteria: known or suspected serious pathology as the cause of LBP (e.g. cancer, infection or fracture). or neurodegenerative disease, or inability to complete the scheduled follow-ups over 1-year.

Intervention:

The trial intervention is an organisational-level intervention that will involve integrating an Australian Health Practitioner Regulation Agency (AHPRA) registered MSK clinician (physiotherapist/chiropractor) within the primary care team for people with LBP.

Control:

Usual GP-led management of LBP

Duration of the Study:

4 years total.

2. BACKGROUND

Low back pain (LBP) imposes an immense burden on individuals and society in Australia and around the world. In Australia, LBP is the leading cause of years lived with disability ¹, costs the Australian healthcare system AUD\$4.8 billion annually ², and is the one of most common reasons for visiting a general practitioner (GP) ³. Further, 70-90% of people will suffer from LBP at some point in their lives, with back problems affecting approximately 16% of the Australian population at any point in time, and LBP is the number one cause of early retirement and income poverty ⁴. Many people with an acute episode of LBP recover quickly (within six weeks); however, ~50% of people have disability after three months and, of these, almost 30% are not fully recovered by 12 months ⁵. LBP often leads to poorer quality of life, psychological distress, and disability ⁴.

Better patient outcomes and more efficient use of resources could be achieved by involving other healthcare providers within the primary care team using a share care model. The use of musculoskeletal (MSK) clinicians such as physiotherapists and chiropractors have been shown to improve patient outcomes for low back pain in primary care settings. However, in Australia, physiotherapist and chiropractors more commonly work in solo practices, not co-located within GP medical practices.

We propose that the use of physiotherapists or chiropractors early in LBP care will assist in the delivery of evidence-based treatments, reduce the burden on GPs, decrease costs for the healthcare system, and lead to better outcomes for patients. We will undertake a cluster randomised trial (CRT) to assess if a novel team-based care approach for people with MSK conditions improves patient outcomes and reduces costs for LBP in the Australian setting.

3. PROJECT AIMS

The overarching goal of this CRT is to evaluate whether integrating a MSK clinician (physiotherapist/chiropractor) within primary care teams for people with LBP and making this clinician available to LBP patients as an early point of contact, will improve outcomes. The specific aims are to determine whether a new model of care for people presenting to primary care with LBP, incorporating a team-based approach, is more effective than usual GP-led care, evaluated over a one-year period, for:

- 1) disability (primary outcome at 3 months), pain intensity, quality of life, global rating of change, patient satisfaction, and adverse events.
- 2) health system and societal outcomes, including healthcare access, GP workload, emergency department visits, diagnostic imaging, opioid medications used, and missed work.
- 3) cost-effectiveness.

Further, a process evaluation will assess the implementation of the model of care and the perspectives of patients and primary care providers towards the model. This current ethics application does not include the process evaluation; we will submit the ethics application for the process evaluation at a later date.

4. PROJECT DESIGN

4.1. Research project setting and participants

The project setting will be primary care sites in Australia. We will allocate sites to either incorporating a team-based approach or to usual GP-led care. Two levels of participants requiring consent include:

- (1) GPs located within primary care sites in Australia
- (2) Patients under the care of GPs within these primary care sites.

See Appendix–PICFs for all Participant Information and Consent Forms.

4.1.1. General practitioner participant recruitment

Planned recruitment is 20 primary care sites across Australia, with at least 2 GPs from each site who are willing to participate. We will recruit GPs within these primary care sites by the following methods:

- 1) **Advertising:** we will place advertisements in primary health network (PHN) newsletters across Australia. We will use the internet to advertise on websites such as the Royal Australian College of General Practitioners (RACGP) or similar, and on social media platforms such as Facebook in order to target GPs who may be interested in participating in the research (Appendix–ADV). We will also run information sessions face to face or online where we will discuss the trial for GPs who are potentially interested in the study.
- 2) **Direct contact:** If one of the research team or our PHN collaborators has a professional contact within a GP practice they will make initial direct contact (phone, email or face to face) to inform the practice about the potential study, provide the PICF, and determine their interest in participating in the study. We may also contact other GP practices where we do not have professional contacts, via email or phone call.

After initial contact, GPs who are interested in finding out more will be provided with a PICF and any questions they have will be answered by the research team before GPs consent to take part in the project. GPs will be screened by an RA for inclusion/exclusion criteria.

A flow chart outlining the precise method of communication and informed consent procedure is outlined in the appendix section, primary care site Consent Flow chart (Appendix–FLOW).

4.1.2. Patient participant recruitment

Twenty GP practice sites will recruit a total of 1,560 participants.

Consecutive patients consulting their GP with LBP and meeting the inclusion criteria for the study will be invited to participate in the trial. Patients will be given a brief description of the

study by their GP and a hardcopy of the Patient Information and Consent Form (PICF) to read and take away and for their consideration.

If patients are interested in knowing more about the study, the GP will ask for patient verbal consent to release contact details, including patient name, mobile number, and email, to a study research assistant (RA). The RA will then contact the patient by telephone within 24 hours of the patient receiving the PICF to discuss the research project and to seek their voluntary participation.

All potential participants interested in participating after being screened by the RA will be provided with an electronic link to the baseline questionnaire and consent form in REDCap. The first page of the questionnaire will state that by completing this questionnaire the patient is giving consent for their baseline data to be used for the purposes of this research. The baseline questionnaire will be immediately followed by the patient information sheet, the trial consent form and the Medicare consent form. Once the trial consent form is completed, the patient is officially enrolled as a participant in the trial. For any participants who do not have access to the internet or would prefer to do the baseline questionnaire on paper or over-the-phone, this can be completed with a RA who will then enter responses into the database. These participants can then choose to either complete the consent form online like other participants or have the PICF mailed to them with the consent form. On returning the signed consent form patients will then be considered participants in the trial.

As this trial utilises a cluster randomised trial design, the primary care sites which the patient attends will have already been randomly allocated to either the comparator or the intervention arm. As such the GP will be encouraged to use one of the following scripts to inform their patient about the trial and the method of treatment and care they will receive if they choose to participate.

A flow chart outlining the precise method of communication and informed consent procedure is outlined in the appendix section, Patient Consent Flow chart (Appendix–FLOW).

4.1.3. Participant selection criteria

4.1.3.1 Practice selection criteria

Practice inclusion criteria: At least 2 GPs from the practice are willing to participate; and the practice can accommodate a trial MSK clinician to coordinate patient treatment.”

Practice exclusion criteria: The practice already has an integrated MSK clinician (physiotherapist or chiropractor) onsite.

4.1.3.2. GP participant selection criteria

GP inclusion criteria: GP works in an eligible practice, and the GP is willing for their practice to be randomised to the intervention or usual care arm.

GP exclusion criteria: working in a practice that already has a physiotherapist/chiropractor integrated into the team.

4.1.3.3 Patient participant selection criteria

Patient inclusion criteria: adults (≥ 18 years) with LBP (with or without associated leg pain) of any duration, who can read, write, and speak in English. We have excluded non-English speaking patients due to the cost burden of employing interpreters at each of the 20 primary care sites. LBP is defined as pain between the 12th rib and the buttock crease.

Patient exclusion criteria: known or suspected serious pathology as the cause of LBP (e.g. cancer, infection or fracture) or neurodegenerative disease, or inability to complete the scheduled follow-ups over 1-year.

4.2. Randomisation

The trial is a parallel arm cluster randomised trial (CRT) with 20 primary care sites randomised 1:1 to either a new primary care model for LBP incorporating a team-based approach, or to usual GP-led care for low back pain. Randomisation of practices, rather than patients, allows MSK clinicians to fully integrate within the primary care team at primary care sites and reduces potential contamination from therapists concurrently managing intervention and control patients. A logic flow model of the trial is included in the appendix (Appendix–LOGIC FLOW).

Practices meeting the inclusion criteria will be sequentially randomised to receive either the intervention of team-based care or the control of GP led care. Stratified randomisation will be used to reduce the probability of baseline imbalance. Practices will be allocated to the intervention and control groups (1:1 ratio using randomly permuted blocks of variable lengths).

Two strata will be defined by whether the practice is in an urban, or regional/rural-remote location. Clusters will be stratified by geographic region using Modified Monash Model (MMM) classification (urban, regional/rural-remote: MMM1, MMM2-5) [7]. A statistician independent of the trial team will computer-generate the allocation sequence. The statistician will be provided with practice identification codes and stratification information.

4.3. Blinding and unblinding

GPs, MSK clinicians and patients will not be blinded due to the nature of the interventions being compared. However, to achieve a level of equipoise rather than blinding, GPs in each intervention arm will be encouraged to use the same amount of enthusiasm when describing the study to patients, and emphasise we do not know which model of care is superior. The GP at the comparator primary care site will explain that the patient will receive a GP-led care model, while at the intervention sites, GPs will explain that the patients will receive a team-based model of care involving a referral to an MSK clinician.

4.4. Interventions

4.4.1. Intervention group

The trial intervention is an organisational-level team-based intervention that will involve integrating an Australian Health Practitioner Regulation Agency (AHPRA) registered MSK clinician (physiotherapist/chiropractor) within a primary care team for people with LBP (see Appendix section for all Patient flow, GP flow, MSK clinician flow charts (Appendix–FLOW)).

Patients with LBP will first see the GP as usual and will then be provided with a rapid referral to see the practice MSK clinician for 2 visits (paid for by the study) as soon as is convenient for the patient, aiming for within 48 hours. The MSK clinicians will either be co-located (onsite at primary care site) or located nearby (depending on the preference of the GP and needs of the patient). While the MSK clinician is providing care, they will keep the referring GP informed about the patient's progress and refer back to the GP as appropriate.

Led by the MSK clinician, the intervention will have four components:

1) Assessment; 2) Individualised self-management intervention; 3) Health services navigation and team collaboration; 4) Providing additional MSK care to specific people as needed.

1. Assessment: the MSK clinician will: take a thorough history; screen for pathology (e.g. cauda equina syndrome, traumatic fracture, cancer); physical and neurological exam; apply evidence-based tools to identify comorbid health conditions (e.g. depression, anxiety) potentially requiring additional care; and use a validated tool (The STarT Back Tool ⁷) that

has been shown to identify risk factors, and overall risk, associated with persistent LBP and disability ⁸.

2. Individualised self-management intervention: Over the two visits, the MSK clinician will provide an individualised intervention based on guidelines for LBP. The intervention will comprise effective communication to validate the patient's experiences and allow the patient to disclose the impact of their LBP on their lives ⁹, cognitive reassurance ¹⁰, advice/strategies to stay active, individually tailored exercises (if indicated) ¹¹, and strategies to manage recurrences or flares ups. The recommendations will be supported with written information provided to the patient.

3. Health services navigation and team collaboration: The MSK clinician will act as the 'case manager' for individuals with LBP, triaging and linking other team members as needed, and regularly communicating with the referring GP. First, the MSK clinician will further screen and identify pathology requiring referral (e.g., malignancy, fracture), and refer appropriately, including back to their GP if necessary. Next, they will identify comorbid conditions that require collaboration with other primary care team members, e.g., people who screen positive for depression or anxiety that appears to be contributing to their pain and disability may be referred to their GP or to a member of a mental healthcare team. The MSK clinician will collaborate with the GP and other team members and identify the appropriate health services (within the team or community) based on assessment findings.

4. Providing additional MSK care to specific people according to their need: The MSK clinician will provide or organise additional care, beyond the two initial sessions, for patients who require ongoing treatment. Care will include evidence-based, guideline consistent management, such as individualised education, exercise ¹¹, and cognitive behavioural approaches ¹². The MSK clinician will determine if the patient requires ongoing care informed by their overall assessment, progress over the 2 sessions and by the patient's score on the STarT Back tool. The STarT Back tool categorises patients with LBP into low, medium, or high risk of persistent pain and disability based on physical and psychosocial risk factors. The recommended matched treatment for low-risk patients is to provide self-management advice and to avoid referral and investigations where possible. This intervention is brief and can take place over two visits. The recommended matched treatment for medium-risk patients is referral for standard community MSK treatment, such as physical therapy or exercise, and the matched treatment for high risk patients is treatment from a MSK clinician with specific training aimed at reducing physical and psychosocial risk factors for chronic pain and disability ¹²; the training sessions for the MSK clinicians will include how to appropriately use the StarT back tool. This stratified approach to care has demonstrated improved function, quality of life, and cost-effectiveness in comparison to usual care in a UK based clinical trial ¹³. The MSK clinician will provide this care, and help patients navigate the available resources.

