4.4.3. Comparison group: usual GP-led care

Usual GP-led care will be provided in the comparison primary care sites. GPs in the comparison group are free to provide the care they would normally provide, including referral to clinicians such as physiotherapists or chiropractors. Interventions provided or recommended by the GP will be recorded and monitored.

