LBP intensity using the Brief Pain Inventory (BPI) severity index ¹⁶. Health-related quality of life: using the European Quality of life questionnaire EQ-5D-5L ¹⁷, which demonstrates good reliability and validity, and is suitable for economic evaluation in LBP ¹⁸. The utility score will be used to calculate quality-adjusted life years (QALY) for our outcome in the economic evaluation. Global rating of change: using an 11-point global rating of change scale (GROC) (-5 to +5) as has been recommended for self-reported rating of change ¹⁹. The Pain Self-Efficacy Questionnaire (PSEQ) will measure psychosocial factors associated with LBP related disability ²⁰ and The Tampa Scale for Kinesiophobia will quantify fear of movement and reinjury ²¹. Patient satisfaction and experience: using an 11-point scale, extremely dissatisfied (-5) to extremely satisfied (+5). Adverse events: using a self-reported adverse events questionnaire consistent with reporting guidelines (Appendix–AE REPORTING) ²².

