4.6. Adverse event reporting

Adverse events will be self-reported by patients during the standard online follow-up. Adverse events (AEs) will be monitored and defined as any new medical condition or exacerbation of an existing condition as reported by the participants during the study.

Questioning of AEs will occur at all follow ups. Serious AEs will also be monitored and are defined as any untoward medical occurrence that results in death, is life threatening, requires hospitalisation or results in significant disability. We will comply with relevant Australian guidelines and requirements for reporting AEs ²⁴.

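### The adverse event definition has no rule for conditions that pre-date enrolment but are first identified afterwards, and only the intervention arm has mandated screening likely to find them

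*Protocol*

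**What the plan says.** - **Definition.** Protocol section 4.6 monitors adverse events "defined as any new medical condition or exacerbation of an existing condition as reported by the participants during the study". It states no onset rule, no relatedness test, and no treatment of conditions that existed before enrolment and came to light later.
- **Collection, both arms.** "Adverse events will be self-reported by patients during the standard online follow-up", and "Questioning of AEs will occur at all follow ups". Section 4.5 describes the instrument only as "using a self-reported adverse events questionnaire consistent with reporting guidelines"; the form itself is in an appendix that is not shown. The outcome table in section 4.5 has the first adverse event question at 2 weeks and none at baseline.
- **Use.** Section 3 makes adverse events a comparative outcome. The new model is to be compared with usual care for "disability (primary outcome at 3 months), pain intensity, quality of life, global rating of change, patient satisfaction, and adverse events".
- **Intervention arm.** The assessment in section 4.4.1 has the MSK clinician screen for pathology and "apply evidence-based tools to identify comorbid health conditions (e.g. depression, anxiety) potentially requiring additional care". Under the navigation component, "the MSK clinician will further screen and identify pathology requiring referral (e.g., malignancy, fracture), and refer appropriately". The first MSK visit is aimed for within 48 hours.
- **Comparison arm.** Section 4.4.3: "GPs in the comparison group are free to provide the care they would normally provide". No screen is required and none is prevented.

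**The concern.** Finding unrecognised comorbidity is an intended product of the new model. The only stated source of adverse event data is the participant, who is not blinded (section 4.3). What a participant has been told therefore affects what is counted. An intervention patient who first hears at the MSK visit that they may have depression can reasonably enter it as new at 2 weeks. A similar patient in a control practice may not have been told, and so would have nothing to enter.

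The same questions put after unequal detection can give unequal answers. At stake is one secondary outcome, the comparison of harms. An excess in the intervention arm would mix true harm with earlier recognition, and section 4.6 asks for nothing that would let the two be separated.

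**Working it through.** The protocol gives no adverse event rate and no detection rate, so there is no stated figure to reproduce. The check has two parts: the text set side by side, and an illustration with assumed inputs.

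**Text**

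1. Does the definition settle the case? It separates a new condition from worsening of an existing one. It does not say which applies to a condition that was present but unrecognised, and it leaves the report to the participant.
2. Is detection equal by design? Required screening for depression, anxiety and pathology appears only in section 4.4.1. Control GPs may diagnose what they would normally diagnose. The difference is one of degree.
3. Does the timing let it matter? The screen is aimed for within 48 hours and the first adverse event question comes at 2 weeks, so findings from the screen can be in hand when the patient first answers.

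**Illustration**

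Denominator, from sections 4.2 and 4.8.1: 10 practices per arm × 78 = 780. With the allowed 20% attrition, 780 × 0.8 = 624 per arm.

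Assumptions (not protocol figures): the true risk of any adverse event, p, is equal in both arms. A share d of otherwise event-free intervention patients report a newly found condition. Usual care surfaces a fraction q of that share.

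- Intervention: p + (1 − p)d
- Control: p + (1 − p)dq
- Spurious risk difference: (1 − p)d(1 − q)

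| p | d | q = 0.5: control vs intervention | q = 0: control vs intervention |
|---|---|---|---|
| 30% | 2% | 30.7% vs 31.4%, difference 0.7 points, ratio 1.02 | 30.0% vs 31.4%, 1.4 points, 1.05 |
| 20% | 5% | 22.0% vs 24.0%, 2.0 points, 1.09 | 20.0% vs 24.0%, 4.0 points, 1.20 |
| 10% | 10% | 14.5% vs 19.0%, 4.5 points, 1.31 | 10.0% vs 19.0%, 9.0 points, 1.90 |

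The first and last rows are the extremes for p from 10% to 30% and d from 2% to 10%. Among 624 patients per arm, the range at q = 0.5 is about 4 (0.007 × 624) to 28 (0.045 × 624) extra patients. At q = 0 it is about 9 (0.014 × 624) to 56 (0.090 × 624).

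For the middle row, take a two-sided 5% test of two proportions by normal approximation, with effective size 624 / (1 + 61.4 × ICC), where 61.4 = 624/10 − 1. At assumed ICCs of 0, 0.01 and 0.05, the effective size is 624, 387 and 153 per arm. The chance of a nominally significant excess with no true difference is about 40%, 27% and 13% at q = 0, and about 13%, 10% and 6% at q = 0.5.

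**The case against.** **The arms are treated alike.** One definition, one self-report route and one set of follow-up times apply to everyone. A control patient newly diagnosed by the GP reports it in the same way. This stands against any reading that such conditions count as harm in the intervention arm only. It does not remove unequal detection.

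**A pre-existing condition is not new.** On its words, section 4.6 would admit such a condition only if it worsened. Section 4.4.1 also says only that people who screen positive may be referred, and only where the problem seems to contribute to pain and disability; a positive screen is not a diagnosis. So the inflation is possible, not automatic. But the classification is left to the patient, and no rule tells them how to make it.

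**Serious events.** A reader might infer that the serious category is equally distorted, since malignancy and fracture are among the conditions screened for. The documents do not support that. Known or suspected serious pathology is excluded in both arms (section 4.1.3.3), intervention patients see the GP first, and detection alone meets none of the serious criteria in section 4.6. This route is secondary.

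**The form may already ask.** The questionnaire is not shown and may record onset or cause. That could make part of the fix unnecessary, but section 4.6 would still need to say how such conditions are classified.

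**Other data may help.** Listing events by type would expose an excess of depression or anxiety. The baseline EQ-5D-5L includes an anxiety/depression item in both arms. Both help, so an excess would not be beyond interpretation. Neither records when the reported condition began or how it was found.

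**Conclusion.** The point holds as a gap in the definition combined with unequal detection by design. Section 4.6 does not say how to handle a condition that began before enrolment and was identified afterwards, and mandated screening makes such findings likely to be more frequent in the intervention arm. The adverse event comparison is open to bias against the intervention, mainly through depression and anxiety.

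The documents do not show that bias will occur, and they do not give its size. The range of 0.7 to 9.0 points rests wholly on assumed values for true risk, detection and control-arm recognition; it shows what is possible and is not an estimate. The primary RMQ comparison is unaffected.

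The matter is still best settled in the protocol. Onset and route of detection have to be asked when the event is reported, and a later analysis plan cannot reliably recover them.

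**What to change.** 1. In section 4.6, and on the adverse event form in both arms unless it already asks, record (a) whether the problem began before or after enrolment and (b) whether it was first found at an assessment for low back pain.
2. Keep the full count of all reported events as the main between-arm comparison.
3. Also report, by arm and type, the conditions that pre-date enrolment and were first identified afterwards, with a supporting comparison that excludes them.
4. Leave serious event reporting unchanged.

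The cost is at most two items on the online form and a short addition to section 4.6. The downside is that onset rests on recall by unblinded patients. Exclusions would probably fall more heavily on the intervention arm, which has more assessments, and could hide real harms. For that reason the comparison without these conditions should be supportive only and should not replace the full count.
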